6.2. KEY DEFINITIONS

6.2.1. Baseline Values

Baseline is defined as the last non-missing value on or prior to the day of the first dose of double-blind study medication. If the first dose date is missing, the last non-missing value on or prior to the randomization date will be used.

6.2.2. First Dose Date

Two “first dose dates” will be required - one for the Run-In period and one for the double-blind treatment period. The first dose date for the Run-In period will be the date of administration of the first dose of single-blind placebo tablets during the Run-In period. The first dose date for the double-blind treatment period will be the date that the first dose of randomized, double-blind study drug is administered. Both first dose

dates will be obtained from the eCRF. Study analyses will use the double-blind treatment period first dose date.

6.2.3. Study Day

Study Day is the number of days starting from the first administration of double-blind study drug, which is counted as Study Day 1. If the assessment date is after the date of the first double-blind study drug, the study day is calculated as date of assessment - date of the first dose administration+1. If the assessment date is prior to the date of the first double-blind study drug, the study day is calculated as date of assessment - date of the first dose administration.

6.2.4. Duration

Duration of double-blind treatment will be determined as Double-Blind Duration = Double-Blind Last Dose Date minus Double-Blind First Dose Date plus 1. Duration of Run-In period will be determined as Duration = Last Dose Date in the run-in period minus First Dose Date in the run-in period plus 1.

6.2.5. End of Study

The end of study is defined as the date of final contact as entered on the End of Study page of the eCRF. Any missing date of last contact on the End-of-Study eCRF will be imputed as the date of last contact recorded in the database.

6.2.6. Patient Years

Patient years are calculated as sum of the duration from first dose of double-blind treatment to the end of study / 365.25 of all subjects in the specified analysis set and treatment arm. This is used as the denominator of the computation of incidence rate.

6.2.7. Intensification of Hypoglycemic Agent Use

Intensification of hypoglycemic therapies should be considered if one or more of the following:

1. A new oral hypoglycemic therapy is added to the prior medication.
2. An increase of dose in any of the prior oral therapies.
3. A new injectable non-insulin hypoglycemic therapy is added to the prior medication.
4. An insulin therapy is initiated in addition or in place of oral hypoglycemic therapy (ies).
5. An increase of ≥ 5 units total daily dose of insulin any time during the treatment period

The following scenarios are NOT considered intensification:

1. A replacement of a sulfonylurea or insulin with an injectable GLP-1 agonist;

2. An increase of < 5 unit of insulin total daily dose;
3. Any increase of the therapy use after the last day of investigational product administration;
4. Insulin dose usage as needed or pro re nata (PRN) will be considered the same dose;
5. A short course treatment of insulin or other therapies to manage an acute illness.
6. An intensification after relaxation will not be considered as intensification.

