4.2 Inclusion Criteria

The study population will include:

1. Male or female adult subjects with an age ≥ 40 years
2. Subjects with a diagnosis of T2DM
3. Subjects with HbA1c values of 7.0 – 11%, inclusive
4. Subjects with fasting plasma glucose (FPG) ≤ 300 mg/dL at screening
5. Subjects who have a regimen for treatment of T2DM that has been stable for the past 3 months. A stable regimen is defined as: no changes in dose or frequency of OHAs or GLP-1 agonists, or $< 20\%$ variability in total daily insulin dose.
6. Subjects who present with at least one of the following 3 histories:

Group 1: A history of atherosclerotic vascular disease as defined by one or more of the following: a) myocardial infarction (MI) or ischemic (non-hemorrhagic) stroke > 3 months but ≤ 5 years prior to screening or b) documented history of coronary, carotid, or peripheral arterial revascularization (coronary artery bypass grafting must have occurred ≥ 5 years prior to screening)

Group 2: A history of NYHA class II or class III heart failure ([Appendix 4](#)) at the time of screening. History of heart failure is defined as:

- a documented left ventricular ejection fraction (LVEF) $\leq 40\%$ and no subsequent LVEF $> 40\%$ documented within 6 months of screening, or
- (i) an NT-proBNP > 300 pg/mL and no evidence of atrial fibrillation/flutter (AF) at the time of the screening ECG or an NT-proBNP > 900 pg/mL and evidence of AF at the time of the screening ECG and (ii) either (a) structural heart disease documented by report of left atrial enlargement or left ventricular hypertrophy, or (b) exhibiting symptom(s) of HF requiring treatment with diuretic(s) for at least 30 days prior to screening.

Group 3: Age \geq 55 years with 2 or more of the following:

- a. diabetes duration of \geq 10 years,
 - b. uncontrolled hypertension defined as SBP $>$ 140 mmHg despite 3 or more anti-hypertensive medications,
 - c. current smoking,
 - d. urine albumin:creatinine ratio (UACR) $>$ 30 mg/g,
 - e. eGFR of 45 to 60 mL/min/1.73 m², or
 - f. HDL $<$ 1 mmol/L (38 mg/dL)

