5.2.5 Rescue Medications for Hyperglycemia

During the treatment period subjects will be advised to conduct daily fasting SMBG measurements. Blood glucose values collected via SMBG will be evaluated at study visits by the investigator. In addition, hyperglycemia will be monitored by FPG measurement at each study visit. HbA1c values will also be available to the investigator for decision-making regarding the need for rescue medication.

If hyperglycemia is identified through SMBG or FPG measurements, the investigator will determine whether the subject has fasted for a minimum of 10 h prior to the morning blood draw to ensure that the FPG value is truly a fasting sample. If proper fasting has not occurred, the subject will be asked to return for a repeat blood test within a week.

During the first 24 weeks of the treatment period, hyperglycemia should be managed with diet and exercise counseling and only with changes in the medical therapy if the investigator feels it is necessary for the well-being of the subject. Intensification of the antidiabetic regimen should adhere to the following guidelines upon the report by a study subject of two fasting blood glucose self-measurements exceeding the following values on consecutive days: (i) ≥ 270 mg/dL (15 mmol/L) from week 1 to week 6; ≥ 240 mg/dL (13.3 mmol/L) between week 6 and week 12; and ≥ 200 mg/dL (11.1 mmol/L) between week 12 and week 24. After 24 weeks changes to the medical therapy for hyperglycemia should occur at the discretion of the investigator based on SMBG, FPG, and HbA1c information using local standards of care for subjects with T2DM. If a rescue medication for hyperglycemia is to be prescribed, a blood sample must be drawn prior to the administration of the rescue medication so that a final HbA1c value can be determined for the HbA1c efficacy analyses.

The investigator may provide rescue treatment with any approved medication for diabetes that is not otherwise contraindicated, with the exception of an SGLT2 inhibitor. Dose or frequency increases in OHA or insulin regimens prescribed prior to screening will be considered rescue medication. During the treatment period, increments or decrements in the doses of OHA or insulin must be documented in the concomitant medications CRF.

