6.2.8. Relaxation of Hypoglycemic Agent Use

Relaxation of hypoglycemic therapies should be considered if one or more of the following:

1. Stop or decrease dose of one or more oral hypoglycemic therapies occur during the double-blind treatment period;
2. A decrease of ≥ 5 unit total daily dose of insulin any time during the treatment period.

The following scenarios are NOT considered relaxation:

1. A decrease of hypoglycemic therapies after an intensification of hypoglycemic therapy use.
2. Stopping of a short course of hypoglycemic therapy use.

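### SAP 6.2.7 and 6.2.8 have no rule for changes to a non-insulin injectable already in use, and leave open whether a frequency-only change of an oral drug counts

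*Combined protocol and SAP*

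**What the plan says.** SAP 6.2.7 lists five events, any one of which is an intensification:

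1. Starting an oral agent that the subject was not already taking.
2. For oral drugs already in use: "An increase of dose in any of the prior oral therapies"
3. Starting a non-insulin injectable; only a new agent counts.
4. Insulin started on top of, or instead of, oral treatment.
5. For insulin already in use: "An increase of ≥ 5 units total daily dose of insulin any time during the treatment period"

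SAP 6.2.8 lists two relaxations. The first is "Stop or decrease dose of one or more oral hypoglycemic therapies occur during the double-blind treatment period". The second is a fall of at least 5 units in the total daily insulin dose. GLP-1 agonists appear by name only once in these rules, in a 6.2.7 exclusion for a sulfonylurea or insulin being replaced by one.

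The protocol is wider in two respects. Its definition of a stable entry regimen in 4.2 includes "no changes in dose or frequency of OHAs or GLP-1 agonists", so GLP-1 agonists are accepted background therapy and dose and frequency are separate attributes. Protocol 5.2.5 states: "Dose or frequency increases in OHA or insulin regimens prescribed prior to screening will be considered rescue medication".

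The endpoints in SAP 4.2 concern additional or reduced anti-diabetic medications, and the objectives in SAP 3.2 refer to the anti-diabetic regimen. Neither is limited to oral drugs and insulin.

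**The concern.** A derived flag should measure the endpoint it is named for. Here one permitted background class can be changed in either direction without meeting any item. For oral drugs, two programmers working from the same data could produce different flags, because the SAP does not say which quantity has to rise or fall. SAP 7.5 records dose and frequency as separate items, so a comparison of the dose field alone would pass over a change made only in frequency.

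The written rule has no stated backstop. The SAP revision history records that adjudication of intensification and relaxation, and later of rescue medication, was removed and a definition supplied. SAP section 12 does not list the omission of frequency among the changes from the protocol.

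At stake are the exploratory regimen endpoints, one model covariate, and the sensitivity analyses that are meant to set aside HbA1c values obtained after intensification.

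**Working it through.** The plan gives no figure for this point, so the check sets typical medication records against the rules and then traces where the flag is used.

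**Records against rules**

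| Change in the record | Item that fits | Result |
|---|---|---|
| Background GLP-1 agonist increased (dose or frequency) | None; 6.2.7 item 3 needs a new agent | Not scored |
| Background GLP-1 agonist decreased or stopped | None; 6.2.8 covers oral drugs and insulin | Not scored |
| Oral drug, same unit dose, once to twice daily | 6.2.7 item 2, only if dose means total daily dose | Open |
| Oral drug, same unit dose, twice to once daily | 6.2.8 item 1, only if dose means total daily dose | Open |
| Extra insulin injection raising the daily total by at least 5 units | 6.2.7 item 5 | Scored, unless a listed exclusion such as as-needed use applies |
| Insulin started in a subject on a GLP-1 agonist and no oral drug | Item 4 does not fit, being tied to oral therapy; item 5 fits once the total goes from 0 to at least 5 units | Scored from 5 units a day |
| New oral drug, new non-insulin injectable, oral drug stopped | 6.2.7 items 1 and 3; 6.2.8 item 1 | Scored |

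**The oral ambiguity in symbols**

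Total daily dose = unit dose × number of doses per day. Going from once to twice daily at unit dose D:

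- Unit dose: D before, D after. No flag.
- Total daily dose: D × 1 = D before, D × 2 = 2D after. Flag.

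The ambiguity can also create a false flag. Going from D twice daily to 2D once daily, the unit dose doubles, but the daily total is D × 2 = 2D before and 2D × 1 = 2D after.

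**Where the flag is used**

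- SAP 8.1.1, primary analysis: HbA1c values after intensification are kept. The flag plays no part.
- SAP 8.2.1.1, main model for the first key secondary endpoint: no exclusion after intensification. The flag plays no part.
- SAP 8.1.2, tipping-point analysis: values after intensification are treated as missing. LOCF analysis: they are replaced. Only intensifications up to week 24 matter here; relaxations do not trigger either step.
- SAP 8.2.1.4: the same sensitivity analyses for HbA1c in the insulin subset.
- SAP 8.2.2.2: a three-level covariate (no change, after relaxation, after intensification), with its treatment interaction, in the HbA1c and FPG models over time. An unscored change leaves the subject at the no-change level.
- SAP 8.2.2.4 and 8.2.2.6: proportions with, and time to first, intensification or relaxation.

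**Availability of data**

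Protocol 5.6 and SAP 7.5 require name, dose, frequency, route, dates and reason for each medication. The missing rules can be programmed from these records.

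**The case against.** The strongest reply is that the rules are broader than a quick reading suggests. A reader might infer that they count only dose changes of oral drugs and insulin and that frequency increases are never scored. The documents do not support that. Added oral agents, added non-insulin injectables, insulin initiation and oral stops are all scored. Insulin frequency increases count through the daily total. An oral tablet taken twice instead of once doubles the daily dose, so item 2 can fairly be read to include it: this is an ambiguity, not an exclusion. Nor is insulin started on a GLP-1 agonist alone simply lost, since item 5 captures it from 5 units a day.

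It is also fair that the dose-or-frequency sentence in protocol 5.2.5 names only oral agents and insulin, so that sentence alone does not make a GLP-1 dose increase rescue. Protocol 6.11 is broader, treating any medication given for hyperglycemia as rescue therapy, but it does not address changes to an existing injectable. The GLP-1 gap therefore rests mainly on the SAP's own endpoints and the background therapy allowed in protocol 4.2.

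Finally, one might expect missed events to shrink the treatment effect. The planned measures are odds ratios and hazard ratios. As an assumed illustration, take true risks of 30% and 15%, with 90% of events detected in both arms and no false positives:

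- Odds ratio with all events: (0.30/0.70) / (0.15/0.85) = 2.43
- Odds ratio with 90% detected: (0.27/0.73) / (0.135/0.865) = 2.37
- Risk ratio: 0.30/0.15 = 2.00 and 0.27/0.135 = 2.00

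With equal detection the main loss is precision. Unequal detection could bias the comparison, but the documents do not show it.

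What remains is that no item covers an existing non-insulin injectable, and that the oral quantity is undefined.

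**Conclusion.** The point holds in limited form. The injectable gap follows from the text with no interpretation needed: permitted background therapy can be increased, decreased or stopped and the subject is still classed as unchanged. The oral point is an undefined term that sits uneasily with protocol 5.2.5. Together they affect exploratory endpoints, one exploratory-model covariate and the HbA1c sensitivity analyses, but not the primary estimate or the main model for the first key secondary endpoint. The exploratory endpoints carry nominal p-values only.

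The size cannot be derived, because the documents give neither the share of subjects on a GLP-1 agonist nor the rate of such changes. A reader might assume that 5% to 15% of the 1650 are on one and that 10% to 30% of these change or stop it over 2 to 3 years. That gives 1650 × 0.05 × 0.10 = 8 to 1650 × 0.15 × 0.30 = 74 subjects. Both percentages are assumptions, so the range shows scale only. It also overstates the reach into the sensitivity analyses, which involve only increases up to week 24, a period in which protocol 5.2.5 discourages medication changes unless the investigator judges them necessary.

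**What to change.** Amend the derivations in the SAP:

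- In 6.2.7 item 2 and 6.2.8 item 1, define oral dose as total daily dose (unit dose × frequency).
- In 6.2.7, add an increase in the total daily or weekly dose of a non-insulin injectable already in use. In 6.2.8, add a decrease in that dose, or a stop.
- Word 6.2.7 item 4 as initiation of insulin in any subject not on insulin.
- Re-derive the flag for 8.1.2, 8.2.1.4, 8.2.2.2, 8.2.2.4 and 8.2.2.6.
- Reconcile 6.2.7 and 6.2.8 with protocol 5.2.5, or declare any remaining difference in section 12.

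The cost is a few lines of SAP text and a programming change using dose and frequency already on the medication CRF. No new data are needed and no treatment rule changes.

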9.5 Primary Endpoints

9.5.1 Primary Efficacy Endpoint

The primary efficacy hypothesis is that bexagliflozin reduces HbA1c after 24 weeks of treatment when compared to placebo. The primary efficacy analysis on change in HbA1c at week 24 is based on the ITT using all observed data. Missing data will be handled using a mixed model repeated measures (MMRM) approach and will include terms for visit, treatment, treatment-by-visit interaction and randomization stratification factors as fixed effects and the corresponding baseline HbA1c value as a fixed effect covariate. Least squares mean treatment differences between the bexagliflozin group and the placebo group will be estimated from the model at week 24 with the corresponding p-values and their two-sided 95% CIs presented. An unstructured covariance will be used to model the within-subject correlation. In the unlikely event the model with the unstructured covariance structure does

not converge, an autoregressive (1) covariance structure will be used. HbA1c values obtained after the start of rescue medication will not be excluded from the analysis.

As a secondary sensitivity analysis, the multiple imputation method will be used to impute missing observations (including observations obtained after rescue medication) prior to carrying out the MMRM analysis. To further examine the sensitivity of the analysis, a last observation carried forward (LOCF) method will then be used to impute the missing observations prior to carrying out the MMRM model.

For supportive analyses, the primary efficacy endpoint will be analyzed with observed available data using the PP analysis sets in a similar manner as above.

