8.1.1. Primary Efficacy Analysis

Let $\mu_{\text{Bexagliflozin}}$ and μ_{PBO} represent the mean changes from baseline in HbA_{1c} at Week 24 for bexagliflozin and placebo arms, respectively. The following hypotheses will be tested:

$$H_0: \mu_{\text{bexagliflozin}} - \mu_{\text{placebo}} \geq 0$$

$$H_a: \mu_{\text{bexagliflozin}} - \mu_{\text{placebo}} < 0$$

Missing data will be imputed via multiple imputations, following which the MMRM will be repeated on the complete datasets with results combined across complete datasets using standard multiple imputations techniques; HbA_{1c} values collected after the start of intensification of hypoglycemic agent will not be excluded. A pattern-mixture model will be used to explore the impact of the missing data. Imputation will be conducted within each treatment arm and subgroup (treatment completer vs. treatment terminated early) under the assumption that non-adherent subjects with missing data will follow the same trajectory of non-adherent subjects with values observed. All efforts will be made to retain subjects in the study. If treatment is discontinued, subjects are encouraged to remain in the study and complete all scheduled visits, including final follow-up visit. However, with all efforts, insufficient values may be available for reliable imputation. This analysis will be performed only if at least 5 subjects in each treatment arm completed scheduled week 24 visit after treatment is stopped. This number is chosen to allow sufficient data to establish a regression model for imputation. For this analysis, the following three-step approach outlined below will be used:

- a. Non-monotone (intermediate visits) missing data will be imputed first using the Monte Carlo Markov Chain (MCMC) method under the MAR assumption in all treatment arms (using the MCMC statement in PROC MI). Multiple chains option

(CHAIN=MULTIPLE option in the MCMC statement of PROC MI) will be used. For the non-monotone imputation of the HbA_{1c} missing data, a multivariate normal model will be used including variables for the HbA_{1c} at baseline and all post-baseline visits within each treatment group. Five hundred imputed datasets will be generated.

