8.1.2. Sensitivity Analyses

Randomized subjects who withdraw consent to participate in the study will not be replaced. The early termination rate is estimated to be 6.5% annually. To the extent possible, attempts will be made to minimize the amount of missing data through measures planned in the study conduct, but if data are missing for the primary endpoints and the first key secondary endpoint (change in HbA_{1c} for subjects who have been prescribed insulin), the number, timing, pattern, and reason for the missing value will be summarized. The reason for missing values will be evaluated to investigate possible implications of missing values for efficacy assessments. The dropout patterns will be assessed by Kaplan-Meier plots, if applicable, to assess whether they differ between treatment arms. If there are missing values for the primary and key secondary analysis, all observed data will be analyzed and data obtained after rescue will not be excluded.

To evaluate the impact from missing data and intensification of hypoglycemic agent, the following sensitivity analyses will be conducted:

- 1) Tipping point analysis will be conducted. Data after intensification of hypoglycemic agent will be considered as missing. Following steps will be followed:
 - a. Create monotone missing data as step a in section 8.1.1;
 - b. Regression approach under MAR will be used to generate complete datasets. The predictors for the regression imputation model at any time point will be region, baseline eGFR categories (<60 or ≥ 60 mL min⁻¹per 1.73 m²), baseline BMI category (< 25 kg m⁻² or ≥ 25 kg m⁻²), history of heart failure (yes or no), insulin use or not, and HbA_{1c} at all previous time points, including baseline. The first imputed values will be penalized or rewarded based on the treatment subject received:
 - Subjects in the bexagliflozin group: missing value will be analyzed assuming the treatment effect is worsened by $\delta 1$ (where $\delta = 0.1$ to 0.5, in step of 0.1) compared to the subjects who have no missing value in the reduction of HbA_{1c} value;

- Subjects in the placebo group: missing value will be analyzed assuming the treatment effect is better by δ_2 (where $\delta = 0$ to 0.5, in step of 0.1) compared to the subjects who have no missing value in the reduction of HbA_{1c} value;

The penalty or reward will not be applied to the values from later time points as these values are penalized or rewarded through regression on previous time points.

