- c. Imputed datasets will be analyzed and results combined as step c in section 8.1.1.

For each combination of (δ_1 , δ_2), 100 imputed datasets will be obtained. These 25 combinations will be separately analyzed to explore under which condition where the null hypothesis can no longer having evidence to be rejected.

- 2) Furthermore, data that are missing or after intensification of hypoglycemic agent will be imputed using LOCF. All observed data and the imputed values will be analyzed using MMRM model. Model as specified in the primary analysis will be used.

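### The tipping-point and LOCF analyses in SAP 8.1.2 keep week-24 HbA1c measured after therapy increases that SAP 6.2.7 does not count as intensification: those after the last study dose or after a relaxation

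*Combined protocol and SAP*

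**What the plan says.** SAP 8.1.2 gives the purpose of its sensitivity analyses: "To evaluate the impact from missing data and intensification of hypoglycemic agent". For the tipping-point analysis, "Data after intensification of hypoglycemic agent will be considered as missing"; the imputed values are then shifted by delta. For the second analysis, "data that are missing or after intensification of hypoglycemic agent will be imputed using LOCF".

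SAP 6.2.7, under Key Definitions, fixes what intensification means. Its list of scenarios that do not count includes "Any increase of the therapy use after the last day of investigational product administration" (item 3) and this rule (item 6): "An intensification after relaxation will not be considered as intensification". Item 6 sets no limit on the size of the increase and does not require that it only restore the baseline dose.

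The primary analysis in SAP 8.1.1 goes the other way by design: HbA1c "values collected after the start of intensification of hypoglycemic agent will not be excluded".

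In the protocol, section 9.5.1 describes a sensitivity analysis in which "the multiple imputation method will be used to impute missing observations (including observations obtained after rescue medication". Protocol 5.2.5 treats dose or frequency increases in pre-screening oral agents or insulin as rescue, and protocol 6.11 treats any drug given for hyperglycemia as rescue. Neither makes an exception for increases after study drug stops or after a relaxation.

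**The concern.** The two analyses in 8.1.2 show what the HbA1c result looks like without values affected by added glucose-lowering therapy. Which values are removed depends entirely on 6.2.7. Items 3 and 6 mean that the same added therapy is handled in opposite ways, depending on whether study drug had already stopped or some earlier dose had been reduced.

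At stake is how far a reader can rely on these analyses. They still contain some post-rescue HbA1c at face value, with no imputation and no delta. The rule carries over to the insulin-subset key secondary endpoint, which is in the testing hierarchy (SAP 8.2.1.4), and to the exploratory sulfonylurea subset (SAP 8.2.2.1).

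**Working it through.** No planned figure bears on this point, so the check is mainly a tracing of rules, followed by an illustrative size.

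**1. Which values are removed.** In 8.1.2 the only triggers are a missing value or a value after intensification. I found no other rule in that section that removes off-drug or post-rescue HbA1c. Four hypothetical subjects, each with a week-24 sample:

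| Subject | Intensification under 6.2.7? | Week-24 HbA1c in 8.1.2 |
|---|---|---|
| Adds insulin at week 11, on study drug, no earlier relaxation | Yes | Missing and imputed with delta, or LOCF |
| Stops study drug at week 10, adds insulin at week 11 | No (item 3) | Kept as observed |
| Reduces an oral agent at week 6, adds insulin at week 11, on study drug | No (item 6) | Kept as observed |
| Reduces an oral agent at week 6, returns to the baseline dose at week 11 | No (item 6) | Kept as observed, reasonably so |

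Rows 2 and 3 are the defect; row 4 is not. A subject with a qualifying intensification before the excluded increase is not affected, because later data are already removed.

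**2. Whether such values will exist.** SAP 8.1.1 encourages subjects who stop drug to complete all visits, and makes its imputation conditional on "at least 5 subjects in each treatment arm completed scheduled week 24 visit after treatment is stopped". SAP 6.4 maps all post-baseline visits with no on-treatment restriction. The last row of SAP Table 6 assigns data more than 7 days after the End of Treatment visit to Follow-up, which could overlap the week-24 window for someone who stopped early. Reading that row as removing off-drug week-24 values would contradict 8.1.1.

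**3. Whether the change is declared.** SAP 12 lists the move to imputation based on retrieved dropouts, the covariate changes and the added exploratory items. It does not mention that post-rescue removal now follows a definition with these two exceptions.

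**4. Illustrative size for item 3.** All three inputs are assumptions. The nearest planning figure, 6.5% early termination a year, gives 1 − 0.935^(24/52) = 3.05% by week 24. It does not count subjects who stop drug and stay in follow-up, so it cannot supply the first input.

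- Share of an arm that stops drug before week 24 and is still sampled: 4% (2 to 8%)
- Share of these who then add therapy: 30% (20 to 50%)
- HbA1c lowering by that therapy: 0.8 points (0.5 to 1.5)

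Share kept at face value = 0.04 × 0.30 = 1.2% of the arm (0.02 × 0.20 = 0.4% to 0.08 × 0.50 = 4%).

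Shift in the arm mean = 0.04 × 0.30 × 0.8 = 0.0096 points (0.02 × 0.20 × 0.5 = 0.002 to 0.08 × 0.50 × 1.5 = 0.06).

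Item 6 would add to this, but the documents offer no basis for its share. Each further 1% of an arm affected adds 0.01 × 0.8 = 0.008 points.

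**5. Scale.**

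- Planning standard error of the difference: 1.1 × √(1/1100 + 1/550) = 0.057, so 0.0096 is about one-sixth of it.
- Planning effect: 0.0096 / 0.22 = 4.4%.
- Planned penalties, assuming 10% of an arm is imputed: one step is 0.1 × 0.10 = 0.01; the largest is 0.5 × 0.10 = 0.05 in one arm, or 0.10 in the difference if both arms are shifted fully.

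**6. Direction.** Values kept in the placebo arm lower its mean and shrink the difference; values kept in the bexagliflozin arm enlarge it. The documents do not show which dominates.

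**The case against.** The strongest reply is that 8.1.2 uses a defined term consistently and never promises to remove every therapy increase. Keeping off-drug values as observed also matches the retrieved-dropout logic of the primary analysis. Protocol rescue is described largely as therapy added while study drug continues (5.2.5, 5.9), and protocol 9.5.2 describes the multiple imputation simply as filling missing endpoint data. The group may be tiny: SAP 8.1.1 provides for fewer than 5 off-drug week-24 completers in an arm, and the SAP revision history records dropping imputation covariates for want of such subjects. With 5 in the placebo arm, the shift is 5 × 0.3 × 0.8 / 550 = 0.002 points.

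The point about size stands, and so does the observation that an increase after a relaxation may only restore the baseline dose. The rest does not remove the inconsistency. Retaining all post-rescue values is already the primary analysis. These two analyses exist to show the contrast, and they treat the same added therapy differently without giving a reason. The protocol's rescue definitions are not limited to subjects on drug.

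A reader might infer more than the text supports:

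- **That items 3 and 6 were written for the exploratory intensification endpoint and carried over by accident.** They sit under Key Definitions, and the revision history speaks of unifying the wording of intensification and rescue medication. The origin is not stated.
- **That item 6 works unequally by arm because relaxation is expected more often on active drug.** The relaxation objective only says the proportion will be measured against placebo; no direction is given.
- **That the sensitivity results are biased in favor of bexagliflozin.** The net direction cannot be determined.

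**Conclusion.** The point holds as a defect in a stated rule. As written, the tipping-point and LOCF analyses keep week-24 HbA1c measured after a therapy increase that followed the last study dose or any relaxation, while removing it after the same increase made on drug with no earlier relaxation. This narrows the protocol's handling of rescue, and SAP 12 does not say so.

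The consequence is limited. The primary analysis does not use this rule to drop data and is unaffected. The effect on the sensitivity estimates is probably small: about 0.01 points in an arm mean, range 0.002 to 0.06. That rests entirely on assumed rates for item 3, with item 6 unsized. The upper end multiplies three extreme inputs. The change is worth making because the rule defeats part of the stated purpose of these analyses and costs little to correct.

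**What to change.** For 8.1.2, and for its reuse in 8.2.1.4 (insulin subset) and 8.2.2.1 (sulfonylurea subset):

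1. Derive a separate date of first increase above the baseline glucose-lowering regimen, regardless of study-drug status or earlier relaxation. Treat HbA1c after that date as missing (tipping point) or replace it (LOCF).
2. Keep the other 6.2.7 exclusions: replacement of a sulfonylurea or insulin by an injectable GLP-1 agonist, insulin increases below 5 units, as-needed insulin, and short courses for acute illness (items 1, 2, 4 and 5).
3. Do not count a mere return to the baseline dose after a relaxation.
4. State in 6.2.7 that items 3 and 6 apply only to the intensification endpoints.
5. Declare the definition in SAP 12.

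The cost is SAP wording and one derived date. Protocol 5.6 and SAP 7.5 already require medications to be recorded through treatment and follow-up, so no new data are needed.
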